7.3.2 Stiffness (B)

B1. Passive Stiffness

Knee flexor passive stiffness will be assessed with the Biodex system, using six, 15-degree amplitude stretches, from a starting position of 90 degrees knee flexion and at a speed of 5 degrees per seconds. Stretches will be separated by between 2-5 seconds, to allow the muscle to relax between each stretch. EMG monitoring will ensure that the muscle is relaxed before a stretch is applied.

B.2 Stretch Mediated Stiffness

Knee Flexor stretch mediated stiffness will also be assessed with the Biodex system using six, 15-degree amplitude stretches, from a starting position of 90 degrees knee flexion. In order to bring about a stretch reflex mediated muscle response this stretch will be carried out at a speed of 75 degrees per second. Again, stretches will be separated by between 2-5 seconds, to allow the muscle to relax between each stretch and EMG monitoring applied to ensure the muscle is relaxed before a stretch is applied.

Total Stiffness

Total Stiffness will be determined from the fast stretch, following removal of torque due to the weight of the leg (estimated via anthropometric data). Offline analysis in Matlab[™] will determine the average torque and position in the 300 ms prior to the stretch onset and 300 ms period immediately after stretch offset and manipulandum as:

Stiffness = $\frac{Change in torque}{Change in position}$

Passive stiffness (assessed following the 5 deg/s stretch) and total stiffness following the fast stretch will be determined. Stretch Mediated stiffness wil be determined as:

Stretch Mediated stiffness = Total stiffness (fast stretch)- passive stiffness.

Mean EMG amplitude in the hamstrings following the mediated stretch stiffness will be determined. Here the EMG signal will be rectified and the onset and offset of EMG activation determined as the point the signal goes above and below a level (mean baseline period + 4 standard deviations). In total four variables will be assessed (Passive Stiffness, total stiffness, stretch mediated stiffness and EMG amplitude).

An exploratory assessment of activation of the gastrocnemius during muscle stretch tests and stretches will be undertaken. Here the amplitude of the EMG activation during each test relative to resting levels will be measured.

7.3.5 Gait Kinematics during 6 Everyday Walking Tasks (EWT)

Gait Kinematics will be recorded with children in bare feet using Promove inertial sensors (Promove Inertia Studios Netherlands Itd). These will be placed on the heel and lateral aspects of the, shank, thigh and posterior aspect of the pelvis (see figure B). EMG recordings using spike 2 software (CED, UK) will be synchronised to the promove recordings(inertia studio software, Netherlands) using trigger pulses generated via the promove inertia gateway.

Promove data will be recorded at 200Hz and exported for offline analysis in matlab. Sagittal plane Euler angles will be determined for the ankle, knee and hip joints and the movement of the pelvis in space will be determined to give an estimate of centre of mass motion.

Participants will the perform the following 6 EWT:

EWT 1 - 5metre level walk: Self-selected speed

EWT 2 - 5metre level walk: Fast speed

EWT 3 – 3.6 metre walk slope up (Complies fully with Building Regulations Document M for dwellings) EWT 4 - 3.6 metre walk slope down

EWT 5 - 3 steps up

EWT 6 - 3 steps down

For safety handrails will be provided for the slope and steps assessment (https://www.disabledaccessramps.net)

Children requiring the use of a walker will use the rails on the steps and slope test and can use their walker on the level surface. A spotter will also provide supervision throughout the EWT. Up to 3 trials will be performed per EWT, to gather a minimum of five steps per task.

The mean amplitude and variability (determined respectively from the mean and standard deviation of 5 steps) of knee flexion in midstance (50% stance phase) and at initial contact will be determined in each condition. Exploratory analysis will assess joint inter-coordination using angle-angle plots. Mean rectified EMG amplitude over a 200 ms window centred on each time point (initial contact and midstance) will be assessed

7.4 Clinical Measures of Impairment

7.4.1 Selective Motor Control (SMC)

SMC will be assessed using the validated, Selective Control Assessment of the Lower Extremity (SCALE) tool. This tool was developed by Fowler *et al.* (2009) for health professionals to clinically assess SMC in the entire lower limb in patients with spastic CP. The SCALE assessment will be completed by the SC with participants positioned on a plinth in sitting, except for the assessment of the hip, which will be performed in side-lying. The assessment will be filmed using 3 static cameras set up to give a 3D view and the video footage will be used by the SC and a blinded assessor to calculate the SCALE score for each participant's lower limb. EMG recordings will be simultaneously assessed to provide an exploratory analysis of muscle activation during this test.

7.4.2 Passive Range of Motion (PROM)

7.4.2 (I) Popliteal Angle

The popliteal angle (assessment of hamstring length) will be obtained from both lower limbs with the participant positioned in supine lying on the plinth. The SC will flex the participants hip to 90 degrees and extend the knee, the research assistant will then record the popliteal angle using a goniometer, in accordance to CPIP measurement guidelines ((APCP, 2017) . This will then be repeated 3 times on each leg, so that an average popliteal angle is obtained for the right and left limb (see figure 3 A).

А

В

Figure 3 A Measurement of popliteal angle 3B Measurement of ankle angle

7.4.2 (II) Passive Ankle Range of Motion

The participant will be positioned in supine on a plinth. The SC will extend the knee and dorsiflex the ankle (assessment of Gastrocnemius length), whilst the research assistant measures the degree of ankle dorsiflexion. This will then be repeated with the knee flexed (assessment of soleus length). Both goniometer measurements will be repeated 3 times, so that an average measure of gastrocnemius and soleus length is obtained for each lower limb (see figure 3B).

8.RECRUITMENT

Recruitment will take place simultaneously across each Child Development Centres (CDCs) and Community Paediatric Outpatient physiotherapy services. These include Plymouth Hospitals NHS Trust, Torbay and South Devon NHS Trust, Royal Cornwall Hospitals NHS Trust. We will also advertise the study via interest groups, University of Plymouth website and charity / support group websites (e.g Cerebra). In preparation for recruitment, the CI will visit each site to familiarise physiotherapists with the eligibility criteria and study procedures

Potential study participants will be identified, screened and recruited as shown in Figure 4.

- Recruitment will take place simultaneously in each NHS trust, the university of Plymouth and via social media
- In preparation for recruitment the SC will visit each recruiting sites to familiarise recruiting clinicians with eligibility and study procedure.

 Once a child has been recruited and identified as a suitable candidate to participate in the study the SC will contact their parents to arrange an appointment for them attend the study assessment at the University of Plymouth

8.1 Estimation of recruitment rate

There are an estimated 1460 children with CP within the targeted age range and severity distribution in the South West of England, based on published prevalence data and population estimates from the Office for National Statistics (2015). Of these 71% of children are predicted to be ambulant, i.e. GMFCS levels I-III. We anticipate that within each NHS trust locality there will be approximately 150 children with a diagnosis of CP (Cerebral Palsy Integrated Pathway South West, 2017 unpublished data). Therefore, we predict that approximately 60-80 ambulant children with CP may be eligible in each NHS trust locality.

We aim to recruit 20 participants with CP across the three sites in Devon and Cornwall over a 6-month period and 20 TDC from the University of Plymouth. An estimated recruitment rate of two to four children per month over a 10-month period has been calculated based on the population and previous experience.

8.2 Participant identification

Recruitment will primarily occur through clinical teams at 3 NHS Trusts: These include Plymouth Hospitals NHS Trust, Torbay and South Devon NHS Trust, Royal Cornwall Hospitals NHS Trust.

Participants will also be recruited via posters and adverts. These will be distributed in local newsletters of groups such as APCP (Association of Paediatric Chartered Physiotherapists) and PenCru (Peninsula Childhood Disability Research Unit). As well as online via social media sites such as facebook, Instagram and twitter on pages that are relevant to our study population, such as Cerebral Palsy UK, Cerebra, CP sport and SCOPE .

- Physiotherapists, occupational therapists, paediatricians and orthopaedic surgeons will identify potential participants during clinics and via their caseload lists. Clinicians may approach children on their caseloads by telephone before sending out an information pack to those who are interested in taking part. The information pack contains a contact reply slip, prepaid envelope and information sheet.
- Posters and leaflets will be produced for clinicians to distribute to potential participants. They will also be issued for clinicians to put up in departments and waiting rooms where children with CP may have appointments.
- Potential participants can contact the research team via contact details on posters / adverts or via a contact reply slip and prepaid envelope which is part of the information pack
- When potential participants contact the research team they will be contacted via their preferred route (eg telephone / e mail) and the participant information sheet

(PIS) will be sent out and later discussed to ensure that the parents / guardian and children understand the study prior to volunteering. The PIS will be available for parents and young adults (16-18 years) and an easy read version will be available for children.

- Consent forms will be provided to parents and, young adults, and assent forms provided to children when attending the appointment.
- Participants / guardians and or parents will be issued with PIS at least 24 hours prior to their study appointment so that they have time to discuss the trial with the research team before participating.

8.3 Screening

The local PI will use a study-specific screening log to record numbers of children eligible, ineligible, the numbers of children approached, and numbers of study information packs given out at each site. Potential participants who respond to the invitation and will be screened for suitability using a telephone questionnaire to check diagnosis, age, GMFCS level, neuromusculoskeletal involvement and distribution and the child's ability to follow simple instructions.

8.4 Payment

Travel expenses (up to £30/visit) will be reimbursed for all assessment sessions. Travel expenses above this amount will be discussed on a case by case basis.

8.5 Consent

- Potential participants/parents and/or guardians will be issued with a PIS
- Discussions will take place between the potential participant, their parent and/or legal guardian and a member of the research team. This will cover the nature of the study, the study procedure, the possible risks associated with participation, as well as their right to withdraw from the study at any time. Potential participants/parents and/or guardians will also be given the opportunity to ask questions.
- According to the Medicines For Human Use (Clinical trials) regulations, children under the age of 16 are prohibited from taking part in a clinical trial without the consent of a parent or legal guardian or representative. Therefore, in children under the age of 16 years old, the child's parents or their legal guardian will be responsible for signing and completing the written consent form. Assent from the child will be obtained through discussion with their parent or legal guardian and the CI.
- Young person's participating between 16 and 18 years of age who are considered capable of giving consent according to the Health Research Authority will have the opportunity to complete their own written consent form.
- Written informed consent and assent will be recorded at the start of the child's study appointment by the CI, before any study investigations can begin.

9. DATA COLLECTION

9.1 Baseline data

- GMFCS level
- Distribution of lower limb weakness
- Date of Birth
- Medical and surgical history
- Height, Weight, pelvic depth

9.2 Outcomes

The trial objectives will be measured using the Outcome measures listed in the table below

	Objectives	Outcome Measures Completed in one study visit		
Prima	Primary Objective			
1.	To explore how variance of knee flexion at initial contact and midstance in children with cerebral Palsy (with and without crouch gait) across 5 Everyday walking trials is best explained by two of the following variables: selective motor control, knee extensor strength, knee flexor strength and knee flexor stiffness	 Selective Motor Control using Selective Control Assessment of the Lower Extremity (SCALE) Knee extensor strength, Knee flexor strength, and Knee flexor stiffness using dynamometer Knee Flexion Angle at Initial Contact and Midstance using Promove, inertial sensors 		
Secon	dary Objectives			
2.	To measure and compare Selective motor control in children with Cerebral Palsy, with and without crouch gait, and in typically developing children.	 Selective Control Assessment of the Lower Extremity (SCALE) Passive Range of motion of the ankle with goniometer 		
3.	To measure and compare isometric and isokinetic knee extensor strength in children with Cerebral Palsy, (with and without crouch gait) and in typically developing children.	 Maximal Isometric and Isokinetic Knee Extensor strength using a dynamometer 		
4.	To measure and assess Isometric knee flexor strength in children with Cerebral Palsy (with and without crouch gait) and in Typically developing children	 Maximal isometric knee flexor strength using a Dynamometer 		
5.	To measure and assess knee flexors passive stiffness, and stretch mediated stiffness, in children with Cerebral Palsy (with and without crouch gait) and in Typically developing children.	 Passive and stretch mediated stiffness of the knee flexors measured using a Dynamometer Passive Range of Motion - Popliteal angle with Goniometer. 		
6.	To measure and analyse amplitude and variability of knee flexion during Initial Contact and Midstance in children with Cerebral Palsy, (with and without crouch gait) and Typically Developing Children	 Knee Flexion Angle at Initial Contact and Midstance using Promove, inertial sensors 		

across five everyday functional walking	
tasks	
Exploratory assessment	
	-
Overflow muscle activation during strength tests	Mean amplitude EMG activation in the
and stretches	gastrocnemius during knee extensor
	strength tests and hamstring stretches.
Muscle activation during SCALE	EMG amplitude and coactivation in the
	hamstrings, quadriceps and gastrocnemius
	during SCALE tasks
Muscle activation during EWT	EMG amplitude and coactivation in the
	hamstrings, quadriceps and gastrocnemius
	during EWT

9.3 Outcome Measures

The following assessments will be carried out at the study appointment. This will take approximately 90 minutes to complete (please see flow diagram- Appendix 2)

9.3.1 Primary Outcome

• Walking Kinematic amplitude measured using PROMOVE inertial sensors over 6 Everyday Walking Tasks.

9.3.2 Secondary Outcome Measures

- Walking Kinematic variability measured using PROMOVE inertial sensors over 6 Everyday Walking Tasks.
- SCALE Selective Control Assessment of the Lower Extremity
- Maximal Isometric and Isokinetic knee extensor strength using Dynamometer (Biodex system 2, Uk) of the most affected limb. Inner and outer range and maximal isokinetic strength.
- Maximal Isometric Knee Flexor Strength using dynamometer (Biodex system 2, Uk) of the most affected limb
- Knee flexor stiffness using dynamometer (Biodex system 2, Uk) of the most affected limb- passive and stretch reflex mediated stiffness and EMG amplitude post-fast stretch
- PROM of the ankle, in a flexed and extended knee position bilaterally using a goniometer
- Popliteal angle of the knee bilaterally using a goniometer

9.3.3 Exploratory Outcome Measures

• Gastrocnemius EMG amplitude will be used to measure over flow activity during strength tests (isokinetic and isometric knee extensor, isometric knee flexor) and fast hamstring stretches.

- Muscle activation during SCALE- EMG amplitude and coactivation in the hamstrings, quadriceps and gastrocnemius will be assessed during SCALE tasks
- Muscle activation during EWT-EMG amplitude and coactivation in the hamstrings, quadriceps and gastrocnemius during EWT tasks

9.4 Withdrawal

Participants can withdraw at any point in the study without giving a reason. It will be emphasised that this would not affect their healthcare or potential involvement in other research. Children's data up to that point will be used for data analysis unless participants express that they would like this data to be destroyed.

10. DATA MANAGEMENT

10.1 Data Collection Tools and source document identification

Study data will be recorded on the trial specific case report forms. The Case report Form (CRF) will be a printed paper document. Data captured on the CRF will be considered source data. The baseline date and outcome measures that will be recorded are outlined in the data management plan.

The study co-ordinator will complete all CRF form for all participants. Completeness of data will be maximised by:

- Checking all forms at the end of the study to ensure no missing items
- Where possible, arranging another assessment session should the participant not attend the scheduled study appointment.

Once study appointment is completed the CRF forms will be signed and dated by the study coordinator.

10.2 Participant Numbering

Each participant will be issued a unique participant number when they are registered onto the study.

10.3 Archiving

Paper and electronic formats and essential study documentation (i.e content of Study Master file) will be store in a secure location for a minimum of 10 years after the end of the study. Archiving will be authorised by the Sponsor following submission of the end of study report. No essential documents should be destroyed unless or until the Sponsor gives authorisation to do so

10.4 Access to Data

Data will be collected and stored in accordance with the Data Protection Act 1998/General Data Protection Regulation 2018. Data generated from this study will be available for inspection on request by the participating research team, Plymouth University representatives, the REC, local R&D Departments and the regulatory authorities.

11. Statistics and Data Analysis

11.1. Analysis of Impairment:

Data will be assessed for normality using a Shapiro-Wilks test. People with CP with and without crouch gait will be compared to TDC using an Analysis of Variance. Significant data will be explored further with post-hoc testing. The following variables will be assessed:

11.1.1 Strength

Isometric knee extensor strength (90 & 30 degrees); Inner and outer range ratio; maximal isokinetic knee extensor strength; maximal knee flexor strength. As strength measures will be related Bonferroni correction will be provided (n=5 variables p=0.05/5=0.001).

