11.1.2 Stiffness

Passive stiffness total, stretch reflex mediated stiffness and EMG amplitude in the hamstrings will be analysed with a Bonferroni correction (n=3 variables p=0.05/3=0.0015).

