11.3 Sample size calculation

Previous work has explored factors affecting stiffness gait in children with CP. Twenty Seven pwCP (age 13.6±8.3 years; gender 15 males, 12 females; height 1.4 ±0.2 metres [m]; weight 39.2± 19.4 kilograms [kg]) were compared to 20 controls. Marked differences in knee strength and stiffness (rectus femoris) were seen between TDC and children with CP with minimal effect sizes of 0.68 (range 0.68-2.2). With 18 people in each group it would be possible to detect a minimum effect size of 0.68. To account for 10% data loss in some measures (e.g. due to participants not completing some tests) we will recruit 20 people with CP and 20 people TDC. With 20 people with CP it will be possible to undertake a multiple regression to investigate factors associated with mean knee flexion amplitude during the EWT and up to two predictors (measures of impairment).

12.SAFETY AND MANAGEMENT OF RISK

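### Both printed Bonferroni thresholds are wrong: 0.05/5 is 0.01, not 0.001, and 0.05/3 is 0.0167, not 0.0015

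*Protocol*

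**What the plan says.** Protocol section 11.1 sets the test for the impairment measures: "People with CP with and without crouch gait will be compared to TDC using an Analysis of Variance". It adds that significant results go on to post-hoc testing.

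Section 11.1.1 lists the strength variables: "Isometric knee extensor strength (90 & 30 degrees); Inner and outer range ratio; maximal isokinetic knee extensor strength; maximal knee flexor strength". It then fixes the level: "As strength measures will be related Bonferroni correction will be provided (n=5 variables p=0.05/5=0.001").

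Section 11.1.2 says that the stiffness measures "will be analysed with a Bonferroni correction (n=3 variables p=0.05/3=0.0015").

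Two other places bear on the stiffness count. Section 7.3.2 says "In total four variables will be assessed (Passive Stiffness, total stiffness, stretch mediated stiffness and EMG amplitude"). Section 9.3.2, the list of secondary outcomes, names three: passive stiffness, stretch reflex mediated stiffness, and EMG amplitude after the fast stretch.

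Section 11.3 gives the design figures: previous differences between CP and typically developing children "with minimal effect sizes of 0.68 (range 0.68-2.2"), and the statement "With 18 people in each group it would be possible to detect a minimum effect size of 0.68".

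**The concern.** Each line prints its own overall level, divisor and result, and in both the result does not follow from the other two figures. An analyst cannot obey both the formula and the number beside it.

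The printed number is a decision rule for the group comparisons under secondary objectives 3 (knee extensor strength), 4 (knee flexor strength) and 5 (knee flexor stiffness). Because only significant results are taken to post-hoc testing, it also decides whether the crouch and non-crouch CP groups are compared with each other on that variable. A strength variable with p = 0.005, for example, passes a true Bonferroni correction but fails the printed one, and goes no further. If the contradiction is settled only after the data are seen, any p-value between the two cut-offs can be called either way.

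**Working it through.** **1. The printed thresholds.** Bonferroni threshold = overall level / number of variables.

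| Family | Level and divisor (source) | Quotient | Printed | Too strict by |
|---|---|---|---|---|
| Strength | 0.05, 5 (section 11.1.1) | 0.05/5 = 0.0100 | 0.001 | 0.01/0.001 = 10 |
| Stiffness | 0.05, 3 (section 11.1.2) | 0.05/3 = 0.0167 | 0.0015 | 0.0167/0.0015 = about 11 |

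The divisor of five agrees with the list in section 11.1.1: extensor at 90 and at 30 degrees, inner/outer ratio, isokinetic extensor, flexor.

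**2. Could another rule give the printed pair?**
- Sidak: 0.0102 and 0.0170.
- Overall level 0.025: 0.005 and 0.0083.
- Overall level 0.01: 0.002 and 0.0033.
- Further division by three pairwise group comparisons: 0.0033 and 0.0056.

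None matches. The printed values would need divisors of 0.05/0.001 = 50 and 0.05/0.0015 = 33. The first looks like a slipped decimal. The second is wrong even after a decimal shift, since 0.015 is not 0.0167.

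**3. Family-wise level as written.** The upper bounds are 5 × 0.001 = 0.005 and 3 × 0.0015 = 0.0045, against an intended 0.05.

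**4. Cost in power.** Evaluable numbers are 18 CP and 18 typically developing children (section 11.3: 20 recruited per group, 10% loss, 20 × 0.9 = 18). The protocol does not give the crouch split, so 9/9/18 is an assumption. So is an equal shift of d standard deviations for both CP groups relative to the typically developing group.

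Three-group ANOVA: F on 2 and 36 − 3 = 33 degrees of freedom, with noncentrality (18 × 18/36) × d² = 9d².

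| d | Strength: 0.01 v 0.001 | Stiffness: 0.0167 v 0.0015 |
|---|---|---|
| 0.68 | 18% v 5% | 23% v 6% |
| 1.0 | 47% v 20% | 55% v 23% |
| 1.5 | 90% v 67% | 93% v 72% |
| 2.2 | over 99% v 99% | over 99% v 99% |

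Simplified check, two-group two-sided t-test: 34 degrees of freedom, noncentrality d × √(18/2) = 3d.

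| d | Strength: 0.01 v 0.001 | Stiffness: 0.0167 v 0.0015 |
|---|---|---|
| 0.68 | 26% v 8% | 33% v 10% |
| 1.0 | 61% v 30% | 68% v 35% |
| 1.5 | 96% v 80% | 97% v 84% |

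In this simplified test, the smallest observed standardised difference that reaches significance rises from 0.91 to 1.20 for strength and from 0.84 to 1.15 for stiffness.

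**5. The stiffness count.** Section 7.3.2 defines stretch mediated stiffness as total minus passive, so total is the sum of the other two. Deriving four quantities and testing three is coherent, and the three in section 9.3.2 match the divisor in section 11.1.2. What remains unclear is the list in section 11.1.2, which runs the words passive stiffness and total together. If a comma is missing there, four variables are listed and the threshold is 0.05/4 = 0.0125.

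**The case against.** The best defence is that little depends on the slip. The error is conservative and cannot create false positives. The level and divisor stand beside each result, so the intended rule is visible. Only secondary comparisons are affected: section 11.2.1 chooses the regression predictors by the largest difference between the crouch and non-crouch groups, not by a p-value. All of this stands, and it limits the point, but it does not make the printed numbers right.

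Three stronger readings are tempting, and the protocol does not support them.

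- A reader might infer that real strength and stiffness differences will in general be missed. Only results with p between the printed and the correct threshold change status. At the top of the range in section 11.3 (2.2), power is about 99% or more under either threshold.
- A reader might infer that the stiffness divisor is also wrong because section 7.3.2 counts four variables. Section 9.3.2 lists three stiffness outcomes, so three is the better supported count. Only a clarification is needed.
- A reader might infer that correcting the thresholds restores power at the minimum effect of 0.68. It does not: even the correct thresholds give only 18% and 23% in the ANOVA illustration.

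**Conclusion.** Wrong as written. Both thresholds contradict their own formulas, by factors of 10 and about 11, and nothing in the protocol justifies a stricter level. The consequence is a loss of power in secondary objectives 3 to 5, together with the loss of post-hoc testing for results that fall between the two cut-offs. At a difference of 1.0 SD, the chance of a significant result is less than half of what the correct threshold would give in the ANOVA illustration.

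The arithmetic is exact and rests on no assumption. The power figures are illustrative: they assume 18 evaluable per main group, a 9/9 crouch split, an equal shift in both CP groups, and the threshold applied to the overall ANOVA p-value. A different split or pattern of means would change them, but not the direction of the loss.

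**What to change.** In section 11.1.1, print 0.05/5 = 0.01 for the five strength variables. In section 11.1.2, print 0.05/3 = 0.0167 and name the three variables as in section 9.3.2: passive stiffness, stretch reflex mediated stiffness and EMG amplitude. State there whether total stiffness, one of the four quantities in section 7.3.2, is derived only or also tested. If it is tested, use a divisor of four and 0.05/4 = 0.0125.

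The cost is two corrected numbers and one clarified list, with no effect on participants, measurements or sample size. It should be done before any group comparison is run, so that the choice of threshold cannot depend on the results.

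### Single-step Bonferroni for the strength and stiffness variables is valid but needlessly conservative; Holm's step-down procedure keeps the same 5% family-wise control and never rejects less

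*Protocol*

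**What the plan says.** Section 11.1 of the protocol sets the test for the impairment measures: "People with CP with and without crouch gait will be compared to TDC using an Analysis of Variance", with post-hoc tests where the result is significant.

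Section 11.1.1 lists five strength variables: isometric knee extensor strength at two angles, their ratio, isokinetic extensor strength and knee flexor strength. It fixes the correction and its reason together: "As strength measures will be related Bonferroni correction will be provided". The threshold printed for the five variables is 0.05/5 = 0.001.

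Section 11.1.2 says that the stiffness and hamstring EMG variables "will be analysed with a Bonferroni correction (n=3 variables p=0.05/3=0.0015". It gives no reason.

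Neither section mentions a step-down procedure.

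The only effect sizes are in section 11.3. They come from earlier work comparing children with CP and controls, which found differences in strength and stiffness "with minimal effect sizes of 0.68 (range 0.68-2.2". The section adds: "With 18 people in each group it would be possible to detect a minimum effect size of 0.68". It states no power, no sidedness and no allowance for multiplicity.

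**The concern.** Single-step Bonferroni holds every variable in a family to the strictest threshold, however clearly the others have been rejected. Holm relaxes the threshold after each rejection and still protects the family at 5%. When several variables in a family show real differences, Bonferroni therefore gives up power on the weaker ones and gains no error control in return. Section 11.3 reports marked differences over a wide range in the earlier data, which is the setting where this could matter.

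The reason given for strength does not favour Bonferroni over Holm. Correlation between tests calls for a method that is valid under dependence. Both methods are, and positive correlation makes Bonferroni more conservative.

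The comparisons affected serve secondary objectives 3 to 5 in section 9.2. With 18 to 20 children per group, power is already scarce.

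**Working it through.** **Inputs.** From the protocol: family alpha 0.05, with five strength and three stiffness variables (11.1.1, 11.1.2); 18 evaluable per group and a smallest effect d = 0.68 in a range up to 2.2 (11.3). Assumed, because the protocol does not give them: two-sided tests, equal correlation of 0, 0.5 or 0.8 between variables, and the pattern of effects within each family.

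**Step 1: the printed thresholds.** 0.05/5 = 0.01, but 0.001 is printed. 0.05/3 = 0.0167, but 0.0015 is printed. Neither reproduces. This is a separate and larger error. Everything below uses the correct divisions, so none of the gain shown comes from repairing it.

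**Step 2: power at a fixed threshold.** For a two-sample t-test, df = 2 × 18 − 2 = 34 and the noncentrality is 0.68 × √(18/2) = 0.68 × 3 = 2.04. Power is the probability that |T| exceeds the two-sided critical value.

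| Per-test alpha | Power at d = 0.68 |
|---|---|
| 0.05 (unadjusted) | 50.9% |
| 0.0167 (correct, stiffness) | 33.0% |
| 0.01 (correct, strength) | 26.3% |
| 0.0015 (printed, stiffness) | 10.0% |
| 0.001 (printed, strength) | 8.0% |

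**Step 3: Holm's thresholds.** Order the p-values from smallest to largest and stop at the first failure. Strength: 0.05/5, 0.05/4, 0.05/3, 0.05/2, 0.05, that is 0.01, 0.0125, 0.0167, 0.025, 0.05. Stiffness: 0.0167, 0.025, 0.05. No step is stricter than Bonferroni, so Holm rejects whatever Bonferroni rejects.

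Error control: if k of the m hypotheses are true, the smallest p-value among them has rank at most m − k + 1, so it faces a threshold of at most 0.05/k. The chance that any of the k falls below 0.05/k is at most k × 0.05/k = 0.05, whatever the dependence.

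**Step 4: bounds on the gain.** The most that Holm can do is test the 0.68 effect at 0.05. The ceilings are 50.9 − 26.3 = 24.6 points for strength and 50.9 − 33.0 = 17.9 points for stiffness. The floor is 0.

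**Step 5: between the bounds.** Simulation, 20,000 runs per setting, 18 v 18, ranges over the three correlations. Power is for a variable with d = 0.68.

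| Family and assumed effects | Bonferroni | Holm | Gain (points) |
|---|---|---|---|
| Strength: other four null | 26% | 26% | 0 |
| Strength: all 0.68 | 26% | 30–33% | 4–7 |
| Strength: three at 0.68, two at 2.2 | 26% | 38–39% | 12–13 |
| Strength: evenly spread 0.68 to 2.2 | 26% | 48–50% | 22–24 |
| Stiffness: other two null | 33% | 33% | 0 |
| Stiffness: all 0.68 | 33% | 38–39% | 5–6 |
| Stiffness: two at 0.68, one at 2.2 | 33% | 44% | 10–11 |
| Stiffness: 0.68, 1.44, 2.2 | 33% | 50–51% | about 18 |

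**Step 6: the planned test.** Section 11.1 plans a three-group ANOVA, not a t-test. Under assumed splits of 18 controls with 9 + 9 CP, 20 with 10 + 10, and 20 with 5 + 15, the pattern is the same: a gain of 4 to 9 points if all effects are 0.68, and 16 to 27 points if the others are larger.

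Under the global null, the five-variable ANOVA family-wise error was the same for both methods: 4.9%, 4.6% and 3.0% at correlations 0, 0.5 and 0.8. With one null variable among large effects, Holm's was 5.0% (strength) and 4.8% (stiffness), at the nominal level within simulation error.

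**The case against.** The strongest reply is that Bonferroni is a legitimate choice. It holds the family-wise error under any dependence, and calling the strength measures related can be read as saying that they form one family needing joint control, which is a conventional reason to correct. That stands: the method is not wrong, and the point is efficiency only.

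Four stronger readings are tempting, and the protocol does not support them.

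- A reader might infer a gain of some 12 to 25 points from the range in 11.3. That range comes from earlier work, where the stiffness measured was of rectus femoris and not the knee flexors, and it is not broken down by variable. The large gains need several other variables to have clearly bigger effects, and 25 is out of reach for a three-variable family. Conversely, the zero-gain case needs the other variables to be null, which would not happen if a minimum of 0.68 carried over to all of them.
- A reader might take relatedness as the stated reason in both sections. It is given for strength only.
- A reader might think that Holm exploits the correlation. It does not, and its error under the global null equals Bonferroni's. A step-down permutation method would use the correlation.
- A reader might think that the primary objective suffers. Section 11.2.1 chooses regression predictors by the largest difference between the two CP groups, not by adjusted significance. Of secondary objectives 3 to 5, only the third is worded as a comparison.

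It is also fair to say that the misprinted thresholds matter more. At d = 0.68, correcting the division alone lifts power from 8% to 26% for strength and from 10% to 33% for stiffness, with no assumption about the other variables. And Holm cannot lift power at 0.68 above the unadjusted 51%.

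**Conclusion.** The point holds as a near-free improvement. Sections 11.1.1 and 11.1.2 commit to single-step Bonferroni, and Holm gives the same guarantee with at least as many rejections on every data set. That comparison needs no assumption.

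The size of the gain does need assumptions. For a 0.68 effect with 18 per group, it lies between 0 and 25 points for strength and between 0 and 18 points for stiffness. It is about 4 to 7 points if all effects are 0.68. These figures rest on two-sided testing, normally distributed measures, assumed correlations and effect patterns, and correctly computed thresholds.

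**What to change.** In 11.1.1 and 11.1.2, replace the Bonferroni correction and its printed thresholds with: *Holm step-down procedure at family-wise 5% within each family, applied to the ANOVA p-values; Holm-adjusted p-values will be reported.* Do not carry 0.001 or 0.0015 into the new text. Holm's first steps are 0.05/5 = 0.01 and 0.05/3 = 0.0167. In 11.1.1, relatedness can stay as the reason for treating the five variables as one family, but not as a reason for preferring Bonferroni.

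The cost is one sentence in each of two sections that have to be corrected anyway, with no extra data or children. The only drawback is that simultaneous confidence intervals are less simple than under Bonferroni, and the plan does not call for them.
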